Protocol

Title: A Non-pharmacological Intervention for Patients With Alzheimer's Disease and Family Caregivers (Care Partners Program)

NCT#: NCT03333252

Date: December 10, 2020

1) Protocol Title

Care Partners Program – CP Program

2) Objectives*

This study protocol describes the study that is sponsored by Florida Department of Health and by the National Institutes of Health/National Institute on Aging. Both entities provide support for the design, conduct, and data analysis of the study.

This study will evaluate the efficacy and feasibility of an innovative dyadic non-pharmacological intervention (DT) that is delivered through an interactive state-of-the-art technology that includes an evidenced-based **caregiver component** modeled after REACH II (Belle et al., 2006) **augmented** by an evidenced-based cognitive and functional training component for the **individual with AD (care recipient)** (Acevedo & [name], 2007; [name] et al., 2004, 2006). The program is designed to: be synergistic; emphasize issues important to caregivers in the earlier stages of caregiving; help the caregiver prepare for caregiving transitions; and engage the caregiver as a therapy extender. The program will be tailored for the CG using a risk appraisal approach (Czaja et. al., 2009) and for the CR. It will also be culturally tailored and based on a community-based and stage-model approach to intervention development. The DT intervention will be compared to a control condition (CC) that includes non-specific mental stimulation for the CR and a nutrition intervention for the CG (we chose this for equivalent contact time). Two hundred and forty dyads will be randomly assigned to the DT or CC conditions. The proposed DT intervention builds on: the findings of our group that specific cognitive training techniques can result in improvement and maintenance of gains in cognitive and functional performance in mild stage AD patients (e.g., Acevedo & [name], 2007); our evidenced caregiver interventions (e.g., Belle et al., 2006); our technology-based interventions (e.g. Eisdorfer, Czaja et al., 2003; Czaja et al., 2013) and our on-going technology-based caregiver intervention program (Caring for the Caregiver Network). **The specific aims** of this project are to:

1) Evaluate the efficacy of the DT intervention on CG outcomes.

Hypothesis 1.1: CGs assigned to the DT condition will demonstrate decreased distress and burden relative to CGs assigned to the CC condition.

Hypothesis 1.2: CGs assigned to the DT condition will experience greater improvements in quality of life, mutuality (quality of the caregiver-patient relationship), and caregiving efficacy relative to CGs in the CC condition.

2) Evaluate the efficacy the DT condition on outcomes for individuals with mild stage AD (CRs).

Hypothesis 2.1: CRs assigned to the DT condition will demonstrate greater improvements in cognitive and functional performance and quality of life and less distress than CRs assigned to the CC condition.

Given our access to diverse populations, we will gather preliminary information on ethnic differences in response to the intervention and the cost and sustainability of the DT intervention. The study will provide critical information for a future larger scale multi-site effectiveness trial. Our goal is to develop a program that is flexible, easily accessible for diverse populations of CGs/CRs and improves outcomes for both members of the dyad, which could ultimately yield significant savings for families and society.

3) Background*

The number of individuals with AD and related dementias is expected to increase significantly in the United States and worldwide in the coming decades with a related increase in burden on the patient, family members and society. Currently, an estimated 5.4 million individuals in the United States are living with AD and estimates suggest that this number will increase to 16 million by 2050. In the state of Florida alone there are 500,000 individuals living with AD and it is anticipated that this number will increase to 720,000 by 2025 (Florida Department of Elder Affairs, 2015; Alzheimer's Association, 2015). Florida has more patients with AD than any other state except California. Alzheimer's Disease is a devastating disease that erodes the quality of life and functioning of the patient, generates high levels of stress and burden on family caregivers, and results in substantial economic burdens to society. AD is also a principal cause of physical disability and institutionalization among older adults. In the U.S. Medicare and Medicaid paid about \$170 billion for care of AD patients in 2014, and by 2050, experts estimate these costs will rise to \$800 billion a year (Alzheimer's Association, 2015).

There is a pressing need to identify interventions that decrease the cognitive/ functional and behavioral manifestations of the disease in the patient, and the distress and health-related consequences experienced by family caregivers. In this regard, vast resources have been directed towards interventions to prevent or cure AD. To date, most of these approaches have been pharmacological and to date most have limited efficacy. While it is imperative to continue these efforts it is also important to explore the efficacy of non-pharmacological approaches to help mitigate the symptoms of the illness. There is an emerging body of research indicating that secondary prevention intervention methods such as cognitive training interventions are effective in patients with mild AD (e.g., [name] et al., 2004; Acevedo & [name], 2007). To date, most cognitive training programs have focused solely on component cognitive abilities (e.g., processing speed), which shows limited transfer to everyday activities. Interventions such as these can be broadened to include functional training (e.g. how to training); procedural memory is generally intact in the early stages of the disease (e.g., Hirono, Mori, Ikejiri, Imamura, Shimomura, Ikeda, et al., 1997). For example, it is feasible to reinforce previously learned procedural tasks or teach new ones such as how to maintain and check a memory notebook. Evidence also indicates that early stage patients can benefit from receiving information regarding their illness and available resources as it enables them to participate in decision-making regarding care choices, which alleviates distress for both themselves and their caregiver. Thus intervening in the early stages of the disease represents “a window of opportunity” for the individual with AD. There have also been a broad range of intervention studies aimed at the caregiver that have shown significant effects in reducing burden, lowering depression, and delaying the placement of patients (Brodaty, Green & Koschera, 2003; Schulz, Martire & Klinger, 2005).

However, there are limitations with current intervention programs for both AD patients and caregivers. For example, existing cognitive training interventions for patients a) typically require multiple sessions of facility- based training, creating logistic barriers for patients and families, b) involve considerable interventionist cost, and c) do not provide the optimal intensity and dosage of treatment. Proven caregiver intervention programs also typically involve home-based therapist visits (e.g., Belle et al., 2006) and many have been evaluated on caregivers of patients in the moderate or severe stages of the disease. Our work and that of others (e.g., Acevedo & [name], 2007; Blieszner & Roberto, 2010) has shown that caregivers of patients with mild cognitive impairments also experience distress, have limited knowledge about dementia and memory impairments, and caregiving. Further, caregiver preparedness in managing the patient's condition is linked to caregiver distress (e.g., Schumacher, Stewart, & Archbold, 2007).

The vast majority of intervention efforts have also targeted only one member of the dyad. We believe that there are important synergies to be gained by treating the caregiver and patient

[figure not shown]
simultaneously in an integrated and an interactive manner. Several studies have shown that there is a reciprocal interaction between the well-being of the care recipient and that of the caregiver (e.g., Lyketsos et al., 2003; Schulz et al., 2008; Terri et al., 1997; Schumacher et al., 2007), and studies have shown that reducing patient distress can reduce caregiver burden (Lyketsos et al., 2003; Terri et al., 1997). In addition, recent data indicates that degree of mutuality (quality of the patient-caregiver relationship) and shared involvement in illness-related care by both the caregiver and patient influence caregiver outcomes (Schumacher et al., 2006, 2007; Berg & Upchurch, 2007). We recently found (Schulz, Czaja, Lustig, Zdaniuk, Martire, & Perdomo, 2009) that an intervention that focused on both Spinal Cord Injured patients and their caregivers resulted in significant improvements in caregivers outcomes when compared to a caregiver only condition and a control condition. To our knowledge, there has been a paucity of research in the dementia caregiver literature that uses an integrated intervention approach.

In the proposed study, we attempt to address limitations of previous research by developing and evaluating the efficacy for both members of the dyad (caregiver and AD patient), of a dyadic integrated innovative technology-based intervention (DT) designed to improve the cognitive and functional status and quality of life of the patient and to reduce burden and distress in the caregiver and improve their quality of life and caregiving self-efficacy. The intervention is also designed to improve the mutuality between the caregiver and patient. The overall paradigm is grounded in theory (e.g, Pearlin et al., 1990; Given, Collins, & Given, 1988, Schumacher et al., 2007), and modeled after a Dual Target intervention developed and implemented by Schulz and Czaja (Schulz, Czaja et al., 2009) for older spinal cord injured patients and their family caregivers (SCI Connect) and our previous research with caregivers and AD patients. Our intervention approach is also consistent with theoretical views that among couples, coping with chronic illness is a dyadic process (e.g., Berg & Upchurch, 2007) and findings that among couples dealing with illnesses, greater collaborative involvement in dealing with problems is related to greater well-being for both members of the dyad (Meegan & Goedderis, 2006). Specifically, the dyadic intervention (DT) represents an integrated dementia management program in which the AD patient will receive cognitive/functional training that is based on an empirically-derived program developed by the team at the University of Miami (UM) and the caregiver will receive a comprehensive intervention package based on the evidenced-based intervention modeled after the REACH II program and modified and implemented in the VideoCare project (Czaja, [name], Schulz, Nair, & Perdomo, 2013) and the on-going Caring for the Caregiver Network study (See Preliminary Studies). The paradigm will also actively engage the caregiver as a therapy extender (deliver the cognitive/functional training) and is designed to promote a collaborative care pattern where the patient and the caregiver work together on strategies to manage the symptoms of the illness (e.g., Schumacher et al., 2007).

The program is synergistic and will be designed so that the caregiver and patient components are mutually reinforcing. We believe that for individuals with an illness or disability and their caregivers, it is important to consider the reciprocal impact that providers and care recipients have on each other in terms of the perception and the emotional and behavioral response to stress and the reciprocal effects of illness (Bookwala & Schulz, 1996; Schulz et al., 2008) (Figure 1). Thus we believe that an intervention that simultaneously targets the caregiver and the care recipient will result in positive outcomes for both members of the dyad. We also believe that the active involvement of the caregiver as a therapy extender for the patient will increase their knowledge of the disease and of the patient's experiences. This will help reinforce information they receive in the caregiver component of the intervention regarding the symptoms of the illness. Further, the knowledge the caregiver gains in the caregiver component of the intervention relating to communication skills will enable them to deliver the therapy more effectively and allow the patient to feel more supported. This should facilitate the patient's involvement in the

cognitive training sessions and encourages practice of the exercises between sessions, which enhances the likelihood of a positive cognitive outcome. The caregiver's active involvement in the intervention will also increase the caregiver's perception that they are engaging in activities, which can actually benefit the patient as opposed to just engaging in symptom management. The interaction between the caregiver and patient in the cognitive therapy process will also enhance feelings of mutuality, which has an influence on perceived burden and caregiver distress (e.g., Schumacher et al., 2007). Improving the skills of the patient may also lessen care demands which will have a positive influence on both caregiver and patient outcomes. A further benefit of the integrated approach is that having the caregiver trained in the provision of the therapy allows for regular and continuous treatment without the need of an outside therapist. This is cost effective, increases adherence, and maximizes dosage effects. Finally, we believe the caregiver's active involvement in therapy will increase the caregiver's perceptions of positive aspects of care provision which is turn linked to level of caregiver distress and patient placement (Schulz et al., 2004).

Figure 1. Conceptual model of stress-health process applied to the care-recipient/patient (left panel) and caregiver (right panel) showing interactive nature of care recipient and caregiver outcome (Adapted from Schulz et al. 2009)

The cognitive component of the intervention ([name], Acevedo, Czaja, & Dura, 2004) will employ a multi-modal approach to train both cognitive and functional skills in mild-stage AD patients. The model focuses on bypassing and compensation for episodic memory deficits mediated by the hippocampus and other medial temporal lobe structures and includes empirically validated techniques such as spaced retrieval (Camp 1989; Camp & Stevens, 1990), dual cognitive support at acquisition and retrieval (Bird & Kinsella, 1996; Lipinska & Backman, 1997), implicit memory/motor learning (Acevedo & [name], 2007; Farina et al., 2002), and employs compensatory techniques such as a memory-notebook system. An unique aspect is a focus on training on procedural and functional skills that have real world relevance ([name] & Acevedo, 2006; [name] & Mogosky, 1999).

The caregiver component of the intervention is guided by the Stress Process Model (SPM) of caregiving (Pearlin et al., 1990), which views the consequences of caregiving as resulting from the interrelationships among several factors including the socio-economic characteristics (e.g., relationship, race/ethnicity) and resources (e.g., social support) of the caregiver, primary (e.g., level of patient impairment) and secondary stressors (e.g., job and relationship difficulties) to which they are exposed, and the caregiver's appraisal of these stressors. It is also guided by transactional models of caregiving (e.g., Schumacher et al., 2006), which include a focus on caregivers and patients as individuals as well as the transactional nature of the relationship between the patient and caregiver. The intervention is also based on a multi-component approach to caregiver interventions and a structured but tailored intervention approach whereby the intervention is tailored to meet the specific needs of the caregiver (Belle et al., 2006; Czaja et al., 2009; Czaja et al., 2013). The intervention is designed to enhance the caregiver's skills and preparedness for the caregiver role, resources available to the caregiver (e.g., social support; knowledge of community resources) and reduce known areas of caregiver risk (e.g., burden, emotional distress).

The integrated intervention approach will also incorporate innovative technology and use state-of-the-art computer tablets as a mechanism for intervention delivery. Use of technology in the context of caregiving with older adults has been found to be feasible, acceptable, and cost-effective across heterogeneous patient and caregiver populations including White Caucasians, African-Americans and individuals of Latino background (Czaja & Rubert, 2002; Eisdorfer, Czaja et al., 2003; Bank et al., 2006; Nichols et al., 2008; Czaja et al., 2013). Technology offers several advantages over traditional intervention approaches. For example, the use of technology allows a "without walls" approach and increases access to information and support. Further, the use of technology offers unparalleled flexibility in the presentation of information. Healthcare professionals can also use technology to monitor the status of the caregiver or the care recipient and deliver an intervention in a cost-effective fashion (Czaja, Eisdorfer & Schulz, 2000; Czaja et al., 2013).

BIBLIOGRAPHY & REFERENCES CITED

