Caregiver Inclusion Criteria:

- MMSE ≥ 26 (with Mungus age and education correction)*
- Providing care for a friend or relative with AD for a *minimum of eight hours* per week for at least the past six months
- Being over the age of 21 years
- Living with or nearby the patient
- Having a telephone
- Planning to stay in the study geographic area for the duration of the study

* For subjects unable to participate in in-person visits, a telehealth version of the MMSE will be given using the same age and education corrected cutoffs.

Exclusion Criteria for Caregiver and Care Recipient Dyads

Exclusion criteria for the dyads include: 1) Presence of significant sensory or motor deficits (e.g., visual or hearing loss, paralysis) in the patient or caregiver that are judged to preclude completion of the study measures; 2) Patient or caregiver is in active treatment for cancer; 3) Patient or caregiver has a terminal illness with a life expectancy of 6 months or less; 4) Patient is in the late stage of the disease, is bed-bound, or nursing home admission planned within 4 months;

5) Procedures Involved*

The study population will include White non-Hispanic, Black/African American and Hispanic caregivers and their loved ones. We anticipate to screen a maximum of 350 caregiver participants. We expect 240 participants (caregiver and care recipient) to complete the study.

The study will be conducted in English or Spanish. We will recruit and randomly assign participants; following a baseline assessment, 240 participants will be enrolled and randomly assigned to one of two groups: 1) Caregiving Condition or 2) Health Promotion (Nutrition) Condition. The entire study is home-based. The intervention will be delivered over 6 months using computer tablet technology in Spanish or English. Assessments will occur in the beginning of the study, 6 months, and 12 months (after completion of the intervention).

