The research team will not use undue influence or manipulation in order to recruit study participants. Our team has extensive experience in recruiting this population and is aware of the ethical conduct necessary to protect human subjects in research. There are regular meeting to monitor recruitment activities to discuss and review our recruitment practices and efforts. During recruitment activities and presentations in community events, the research team provides and explains the content of the flyer to potential participants, and answers and clarifies any questions/ concerns that potential participant may have. Interested participants are instructed and directed to call the phone number or send an email to the address display in the flyer.

11) **Setting**

The study takes place at the University of Miami Miller School of Medicine Center on Aging and the Weill Cornell Medicine Center on Aging and Behavioral Research and in the participants' homes. The intervention is technology-based, thus facilitating the communication and interaction between RAs and participants. Only study assessments (baseline, 6th month, and 12th month) and select sessions may take place at the participant's home.

In cases where a participant is unable to complete a follow-up assessment in-person, a subset of the assessments will be done by phone in order to obtain outcome measures at the proper timepoint.

12) Resources Available

All the study personnel have their CITI certificate. The PI holds regular meetings with the study coordinator and data manager to review the progress of the study. At the same time, there are weekly meetings on data management and recruitment of participants. There is also a weekly clinical team meeting of assessors who are working one-on-one with the participants to monitor and review the progress of the participants.

The Center on Aging and the Weill Cornell Medicine Center on Aging and Behavioral Research lead by [name] has extensive experience conducting research studies. Most of the members of this study are involved in other on-going studies at the Center. The Center has a computer dedicated to store and process the data. It also has secure room and cabinets to store study-related documentation. In addition, the study team contains assessors who are fully bilingual. They are fluent in both English and Spanish, thus capable of implementing the study in either language.

13) Prior Approvals

NA

14) Recruitment Methods

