After IRB approval the research team will contact potential recruitment sites and inform them about the study. These sites will be provided with IRB approved promotional materials (flyer) for recruitment. At the same time, the WCM PR department will be informed and notified of the ongoing research. The PR department will be provided with the promotional materials for the study. WCM sites such as those that make regular postings and newsletters will also be contacted and provided with an approved ad or communication regarding the project. The CITI certified staff members within the project plan to also attend health fairs and /or senior centers and events and have flyers available at various community centers so that potential participants can learn of the study. The WCM approved ad will also be posted in non-WCM newsletters and advertisement sections. Promotional material used in this study are: flyer, radio ad and advertisement blurb.

IRB-approved letters may be sent to designated patients from WCM/NYPH clinics with IRB approval.

Once potential participants learn of the study, they will phone the recruitment phone line. A brief telephone interview will be conducted. If these participants are eligible for the study, they will then be scheduled for the baseline assessment.

Participants will not have any financial liabilities for participating in the study. The study provides financial compensation for their time/effort in completing the assessment. Eligible caregiver participants will receive \$30 for each completed assessment, for a total of \$90 (\$30 at baseline, 6-month, 12-month visits). Eligible care recipient participants will receive \$20 for each completed assessment, for a total of \$60 (\$20 at baseline, 6-month and 12-month visits). \$10 will be provided to those that do not meet eligibility.

15) Local Number of Subjects

We anticipate to screen a maximum of 350 participants. We expect 240 participants (120 dyads) to complete the study. 80 participants will be from University of Miami and 160 will be from the Weill Cornell Medicine Center on Aging and Behavioral Research.

16) Confidentiality

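### Section 2 randomises 240 dyads, but section 15 sizes the whole trial at 240 persons (120 dyads), and nothing reconciles the two

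*Combined protocol and SAP*

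**What the plan says.** Four places in the combined protocol and SAP bear on the size of the trial.

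- Section 2 (Objectives): "Two hundred and forty dyads will be randomly assigned to the DT or CC conditions".
- Section 5 (Procedures Involved): "240 participants will be enrolled and randomly assigned to one of two groups", and also "We expect 240 participants (caregiver and care recipient) to complete the study".
- Section 15 (Local Number of Subjects): "We expect 240 participants (120 dyads) to complete the study". It then gives the split by site: "80 participants will be from University of Miami and 160 will be from the Weill Cornell Medicine Center".
- Section 11 (Setting) names the same two centres and no others: "The study takes place at the University of Miami Miller School of Medicine Center on Aging and the Weill Cornell Medicine Center on Aging".

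The screening ceiling appears twice with different labels: "We anticipate to screen a maximum of 350 caregiver participants" in section 5 and "We anticipate to screen a maximum of 350 participants" in section 15.

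Section 7 (Data Management), which holds the analysis plan, gives no power calculation, target effect, retention rate or significance level for the hypothesis tests.

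**The concern.** Section 2 and section 15 give different sizes for the same trial, and the difference is a factor of two. The dyad is what is randomised, and each dyad supplies one caregiver and one care recipient. The number of dyads is therefore the independent sample size for both the caregiver aim and the care recipient aim. If 120 dyads is also the number randomised, the trial carries half the information that section 2 implies.

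Because there is no sample size justification, a reader cannot work back to the intended count. The recruitment target, and any later statement that enrolment was complete, depend on which section is followed. The planned race/ethnicity effects and treatment-by-race interactions would be strained further by the smaller count.

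**Working it through.** **Reproducing the stated totals.** Section 15 is consistent within itself: 80 + 160 = 240 persons, and 240 / 2 = 120 dyads. Section 2 gives 240 dyads × 2 = 480 persons. Neither total can be derived from design inputs, because none are given.

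**Can the two be reconciled?** Three readings were tried.

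1. *Randomised against completing.* The loss needed is 1 − 120/240 = 50%. Going the other way, with dyads randomised = 120 / (1 − loss), rounded up to an even number:

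| Assumed loss | Dyads to randomise for 120 completers |
|---|---|
| 10% | 134 |
| 20% | 150 |
| 30% | 172 |
| 40% | 200 |
| 50% | 240 |

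   Only 50% gives 240. Section 5 also uses 240 participants both for those randomised and for those expected to complete, which leaves no room for such a loss.

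2. *Section 15 as one site's share.* Its heading says local, but it allots all 240 to the two centres in section 11. No further site is named that could hold the other 120 dyads.

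3. *Participants meaning dyads.* Section 5 alone permits this, but section 15 equates 240 participants with 120 dyads. Elsewhere the word covers caregivers only (the recruitment paragraph of section 5) and care recipients as well (the payment paragraph of section 14), so usage does not settle the unit.

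Section 5 conflicts with one of the other two sections whichever way it is read. If its 240 counts persons, it disagrees with section 2. If it counts pairs, it disagrees with section 15.

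**Screening ceiling.** If 350 counts caregivers, 240 dyads needs a yield of 240/350 = 69%, which is possible. If it counts persons, 350 / 2 = 175 dyads, fewer than 240. This is a missing unit label and not a second contradiction.

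**Size of the effect (illustration).** Assumed: unadjusted two-sample t-test, two-sided α = 0.05, 80% power, 1:1 allocation. The normal approximation is d = (1.960 + 0.842) × √(2/n), with n dyads per arm:

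- n = 120: 2.802 × √(2/120) = 0.362
- n = 60: 2.802 × √(2/60) = 0.511

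The t-test versions are 0.363 and 0.516, a ratio of 0.516/0.363 = 1.42. This is the case in which 120 is also the number randomised, with no loss under either count.

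If 120 is the number completing, it should be compared with the completers from 240 randomised. The retention rates below are assumed:

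| Retention of 240 | Completing dyads | Per arm | d (t-test) | 0.516 / d | 120 as share of completers |
|---|---|---|---|---|---|
| 90% | 216 | 108 | 0.383 | 1.35 | 56% |
| 80% | 192 | 96 | 0.406 | 1.27 | 63% |
| 70% | 168 | 84 | 0.435 | 1.19 | 71% |

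The gap narrows as loss rises and disappears at 50%.

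**The case against.** The best defence is that this is a slip in one word. Sections 2, 5 and 15 all carry the number 240 and only the unit differs, so one wrong noun in section 2 or one wrong parenthesis in section 15 would explain it. The lost information would then be conditional and not demonstrated. That is fair, and the protocol does not show which section is wrong. It does not remove the contradiction, because the possible slips lead to trials of different size.

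The sections also describe different stages, randomised in section 2 and completing in section 15. That is true, but it reconciles them only at a loss the protocol never states.

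The evidence on section 5 is mixed. Its consent paragraph uses the same caregiver-and-care-recipient parenthesis for individuals, which favours persons and would make section 2 the outlier. Its screening ceiling in caregivers fits 240 pairs. Neither settles the matter.

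The t-test figures are not this trial's precision, since the planned analysis is a longitudinal mixed model and every test setting and retention rate above is assumed. That stands. What rests on the documents alone is the factor of two in dyads; at equal retention this implies a ratio of about 1.4 in detectable difference.

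Finally, the text of section 19 on documenting consent was not in the copy reviewed. It is an unlikely place for sample size wording, but it could not be checked.

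**Conclusion.** The concern holds. The stated size of the trial is contradictory: 240 dyads (480 persons) in section 2 against 120 dyads (240 persons) in section 15, with section 5 unable to agree with both. No available text reconciles them, and the randomised-versus-completing reading would require 50% loss.

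Under the assumed test settings, the consequence ranges from a detectable difference about 1.4 times larger, if 120 dyads is also the number randomised, to 1.19 to 1.35 times larger, if 120 is completers and 70% to 90% of 240 would be retained. Which total was intended cannot be determined from the protocol. The figure must be corrected because the recruitment target and the precision of both aims depend on it.

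**What to change.** State one total in dyads, worded identically in sections 2, 5 and 15, with dyads randomised given separately from dyads expected to complete. Label the 80 + 160 site split and the 350 screening ceiling in the same unit.

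- If section 15 reflects what the sites are recruiting, correct section 2 to match. The cost is wording, plus acceptance that precision is less favourable than section 2 implies.
- If section 2 is right and 80 + 160 already counts dyads, correct the 120-dyad parenthesis and the unit in sections 5 and 15. The cost is wording only.

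If 80 + 160 counts persons, meeting section 2 would mean 160 + 320 persons and twice the recruitment at each site. This point does not ask for that. It asks that the protocol carry one consistent count and that the precision it gives be stated plainly.
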